OBSERVATIONAL STUDY PROTOCOL

Version 02 of 9.10.2022

TITLE OF THE STUDY

Italian Registry of Patients Suffering from Chronic Pain

ACRONYM OF THE STUDY:

REALIZER (Italian Registry of Chronic Pain Patients)

PROMOTER: SIAARTI

Coordinating Centre: IRCCS Maugeri Pavia

Introduction

This protocol defines the role and type of database that is intended to be established by SIAARTI.

This registry involves the prospective collection of data from subjects suffering from Chronic Pain of any origin.

Participation in the study requires each subject to sign an informed consent form.

In this protocol the terms Registry and Database will be considered synonymous.

In this project there will be 3 phases:

PHASE 1

Pilot project (3 months): Participation of 7 centers proposing the project. Objective: structuring of the dataset and data entry methods. Dissemination of the project.

PHASE 2

Project extended to centers that wish to collaborate (24 months): Centers participate on a voluntary basis and are distributed evenly across Italy. Objective: full operation of the register to meet the objectives of the project.

FASE 3

SIAARTI promotes the register at the institutions for the establishment of a national register compliant with the DECREE OF THE PRESIDENT OF THE COUNCIL OF MINISTERS March 3rd, 2017 “Identificazione dei sistemi di sorveglianza e dei registri di mortalita', di tumori e di altre patologie. (17A03142) (GU Serie Generale n.109 del 12-05-2017)”

Table of Contents

1. RATIONALE TO SUPPORT THE ESTABLISHMENT OF THE DATABASE.....	5
Description of the purposes of the database	6
2.OBJECTIVES.....	7
Primary Outcomes	7
Secondary Outcomes	7
3. STUDY DESIGN.....	7
Setting	8
Participating Center	8
Deviations from protocol	9
Criteria for abandoning the ongoing study	9
Ending the Study	9
4. STUDY POPULATION.....	9
Inclusion Criteria	9
Exclusion Criteria	9
Description of the pathologies being studied	9
5. PROCEDURES EXPECTED AND INFORMATION COLLECTED.....	9
Enrollment procedure	9
Follow-up procedure	10
Data collection	10
Data collection methods and anonymization	12
Data management and storage	13
Data ownership	13
Subsequent use of the data	13
Archiving	13
6. ENDPOINT	13
Primary Endpoint	13
Secondary Endpoint	14
7. INFORMED CONSENT.....	14
8. STATISTICAL ANALYSIS.....	15
Sample size	15

1. RATIONALE TO SUPPORT THE ESTABLISHMENT OF THE DATABASE

The IASP (International Association for the Study of Pain) defines pain as an unpleasant sensory and emotional experience associated with actual or potential tissue damage or described in terms of such damage¹. The physiological function of pain is to serve as a warning sign of a medical condition or injury. In these cases, treatment of the underlying medical condition is critical and can resolve the pain. However, pain may persist despite adequate management of the underlying condition, or the underlying medical condition may not be successfully treated. If the pain persists or recurs for more than three months, the pain is defined as chronic^{2,3}. Long considered a non-life-threatening condition and often overlooked, persistent pain over time can actually become the sole or predominant clinical problem in some patients, generating a chronic condition that significantly impacts patients' quality of life through a wide range of negative physical, psychological and functional effects that limit social participation^{4,5,6}. For this reason, chronic pain is a condition that deserves a specific diagnostic evaluation and appropriate therapeutic efforts, integrated in a multidisciplinary context of physical and psychological rehabilitation. According to many authors, access to adequate pain care should be considered a human right^{7,8}. Recent observations have highlighted a worrying prevalence of pain throughout the world, with significant variations between countries (ranging from 9, 9% to 50.3%)⁹. For this reason, and due to the impact that chronic pain has on healthcare spending, adequate pain control is considered a global health priority. In fact, chronic pain causes the greatest loss of productivity compared to any other health condition¹⁰ and constitutes a significant share of healthcare spending with costs reaching 3-10% of the gross domestic product of European countries^{11,12}.

An important milestone in the European health regulatory framework is represented by Law 38/2010, which established the citizen's right to not suffer¹³. The law paved the way for recommendations to develop structures dedicated to palliative care and pain therapies and to organize hospital and outpatient facilities to guarantee diagnostic-therapeutic continuity for patients with chronic pain. Nonetheless, the provision of adequate care appears difficult to apply

in our country. Recent data puts Italy in third place in Europe in terms of prevalence of chronic pain (around 24%),¹⁴ and at least a third of patients suffering from it remain without a diagnosis or suffer a significant delay in referral to pain management clinics^{15,16,17}. One of the reasons this happens could be found in the poor implementation of pain therapy networks in the various Italian regions caused by the lack of knowledge of the influx and need for pain therapy centers. For these essential resources to streamline clinical care pathways in the effort to manage chronic pain, it is necessary to understand the needs of the population. The epidemiological data available are mostly retrospective, collected on a regional basis and not across the entire territory, and are often incomplete or collected with methodological biases that do not make them usable for public health purposes. Furthermore, there is no clear clinical characterization of the patients who are referred to pain therapy centers to estimate the actual needs and effectiveness of the proposed treatments. In addition, there are no epidemiological data on the distribution of chronic pain and the association with potential risk factors in Italy, as there is no epidemiological register on the regional or national level.

Clinical registries play an important role in monitoring diseases and healthcare delivery patterns. They represent the starting point for generating "real-world" evidence and for evaluating the impact of treatment and service delivery models on health outcomes. Registries are useful tools for directing projects to improve the quality of care to improve healthcare processes, adherence to guidelines and standards of care, and, ultimately, to optimize the costs of providing care. It has also been demonstrated that the establishment of clinical registries has a significant positive impact on outcome¹⁸.

This project aims to create an Italian registry of patients suffering from chronic pain with the aim of collecting clinical, epidemiological and outcome information on subjects belonging to pain therapy centers on a regional basis as part of the pain management assistance.

Description of the purposes of the database

The purposes for establishing this database are the following:

- continuously and systematically collect, evaluate, and archive relevant demographic and clinical information on patients belonging to chronic pain treatment centers, making it available for studies and research.
- promote the use of uniform and comparable classification systems, definitions, and records in the structures participating in the database.

- Define the flow of patients referring to pain therapy centers to allow adequate health planning and the priority areas of intervention of the national health plan.

The data collected will facilitate the planning of future studies aimed to:

- define the impact of chronic pain at a local and national level, and its territorial and temporal variations over time, through prevalence and incidence measures;
- identify clinical subtypes, risk factors, predisposing and triggering factors;
- increase knowledge in the field of chronic pain to standardize diagnostic/therapeutic pathways and promote adequate management strategies.

2. Objectives

Primary Outcomes

Identify the profiles of patients belonging to pain therapy centers in terms of:

1. Location and type of pain
2. Prescribed therapies
3. Effectiveness of therapies
4. Time needed to reach the efficacy outcome

Secondary Outcome

1. Evaluate the proportion of patients who reach the outcome of 30 or 50% improvement
2. Evaluate the healthcare resources used in terms of number of visits and time needed to achieve the best outcome (30 or 50% improvement)
3. Identify patient profiles that are related to clinically significant outcomes and the specific treatments performed, plus their intermediate surrogate outcomes in relation to specific patterns

4. Describe the relevant clinical variables in the study population. In particular, the absolute and relative frequencies of those clinical variables relevant to the effectiveness of the treatment will be described, categorized by type of treatment, and the timing of the start of treatment with respect to the onset of pain. The data collected may be used for predictive analyses.

3. Study Design

This is a prospective, multicenter, non-profit observational cohort study. No intervention on patients outside of common clinical practice is envisaged.

The study is divided into three phases.

Phase 1, expected to last three months, involves the participation of 7 centers proposing the project and aims to structure the dataset and data entry methods. Actions will also be implemented for dissemination of the project by trying to recruit centers distributed across the national territory. Estimated start date 01/03/2023.

In phase 2, the project expands to the centers that wish to join, and this protocol will be fully operational.

The duration of phase 2 is two years and six months, presumably starting from 01/06/2023. Patient enrollment at each center will begin at different times depending on the rollout of the registry and local ethics committee approval. It is likely that the first patient will be prospectively enrolled in 01/06/2023. The last patient will be enrolled by 01/03/2025 and it will be possible to enter data and follow-up until 01/09/2025. The results of this study will be available by 01/12/2025.

Once the patient has been enrolled, it will be possible to trace the patient's personal file and update it at each follow-up until the end of enrollment.

In phase 3, SIAARTI will promote the register at the institutions for the establishment of a national register compliant with the DECREE OF THE PRESIDENT OF THE COUNCIL OF MINISTERS 3 March 2017 "Identification of surveillance systems and registers of mortality, tumors and other pathologies. (17A03142) (GU General Series n.109 of 12-05-2017)"

Setting

The study aims to collect demographic and clinical data from patients belonging to pain therapy centers recognized at the regional level and belonging to the pain therapy networks established in compliance with law 38/2010 and according to the Agreement between the Government and the Regions of 25 July 2012.

Patients will be registered regardless of the access modality (outpatient or hospitalization) and will be characterized by pathology and treatments performed. The participation of centers for the treatment of pediatric pain is expected. Data relating to patients under the age of 18 will be analyzed separately.

The database aims to follow the patients enrolled according to a code that makes them anonymous.

Participating Centers

The dissemination phase constitutes an integral part of the study and is not possible to predict the definitive number of centers involved. Key professionals have been contacted who will be responsible for the dissemination and implementation of this study based on each center's records. The ethics committee of the coordinating center will be regularly updated by the Principal Investigator as new centers join the study.

The complete list of centers involved initially is reported on the title page of the protocol.

Deviations from protocol

Any deviations from this protocol will be reported to the local Ethics Committee (EC) by the Principal Investigator by sending a request to modify the protocol. This request will be examined by the CE according to local/internal regulations.

Criteria for abandoning the ongoing study

The patient can renounce participation in the study at any moment by withdrawing informed consent. The data collected may be kept if made completely anonymous and if previously authorized by the patient.

Ending the study

In addition to reporting the start and end dates of the study for monitoring purposes, the Principal Investigator will inform the EC of an early termination of the study and the related reasons.

4. STUDY POPULATION

The Registry data will be collected by the structures involved in the management of patients suffering from chronic pain, regardless of the cause. It is necessary to keep the inclusion criteria as broad as possible to obtain a real picture of clinical practice at a national level.

Inclusion criteria

- Subjects > 4 years old
- NRS > 4
- Diagnosis of Chronic Pain according to the IASP19 criteria
- Adherence through written informed consent to participate in the study

Exclusion criteria

- Patients suffering from psychiatric pathology or severe cognitive impairment for which the enrolling doctor does not believe it is useful for the purposes of the study
- Patients unable to sign the informed consent

Description of the pathologies being studied

Adult patients will be enrolled, diagnosed with Chronic Pain (pain lasting > 12 weeks), regardless of the etiology, modality, and age of onset.

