5. PROCEDURES EXPECTED AND INFORMATION COLLECTED

Enrollment procedure

Adult patients of both sexes who belong to pain therapy centers with a diagnosis of Chronic Pain (pain that lasts > 12 weeks), regardless of the etiology, modality and age of onset, will be considered eligible for enrollment.

It will be possible to enroll patients during their first visit (FIRST ANESTHESIOLOGICAL VISIT), or during a check-up visit (ANESTHESIOLOGICAL CHECK-UP VISIT) or during a scheduled hospitalization for pain procedures (ORDINARY OR DAY HOSPITAL ADMISSION)

Patients will be asked to join the study after having been informed in detail (also with the aid of a written information form) of the objectives of the project, as well as the methods with which these objectives will be pursued. Participants will be informed about the lack of informative feedback regarding the results of future clinical evaluations: the results of any research originating from the register, in fact, will not be delivered to the participants themselves. The subject who freely accepts will authorize the inclusion of their data in the project by signing the informed consent form of which they will receive a copy. It will also be clearly explained in the information sheet attached to the informed consent that each participant will have the possibility of withdrawing their participation from the study at any time, without providing any reason and without this jeopardizing the doctor-patient relationship with the specialists involved in the project.

Patients will be informed by the manager of the patient's pain center or the principal investigator for the center (assuming this is not the same individual).

The doctor will complete the electronic CRF after evaluating the patient and classifying him according to the criteria of the IASP (International Association for the Study of Pain) in terms of primary or secondary chronic pain. In the case of a patient enrolled during a check-up or during hospitalization, all data relating to the time in which the patient is in care at the center, the

invasive procedures previously undertaken, the drugs prescribed, will be collected. Retrospective data (only for patients already being treated at the center) will be collected according to a predefined group (e.g.: the patient has been in the care of the center for: > 5 years; from 1 to 5 years; from 1 year to 6 months; from 3 to 6 months; < 3 months).

[figure not shown]
Follow-up procedure

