7. INFORMED CONSENT

Patients enrolled in the study will be given a complete and exhaustive explanation about the nature, purposes, possible risks, and benefits of the study. The patient will be informed that he/she will be free to stop the study at any time. The patient will be given the opportunity to ask questions and will be given as much time as desired to evaluate the information provided. For the pediatric population, consent will be requested from parents in the same way.

The investigating doctor will keep the original of the signed written informed consent.

In the written informed consent form it will be specified that the study data will be stored in computerized form and that the confidentiality of the data itself will be maintained in accordance with the provisions of current legislation.

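### The protocol admits minors in three places but names adult patients as those to be enrolled in two others, and nothing says which rule governs

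*Protocol*

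**What the plan says.** Three places put minors in scope:

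- Section 4, Inclusion criteria: "Subjects > 4 years old".
- Section 3, Setting: "The participation of centers for the treatment of pediatric pain is expected", and "Data relating to patients under the age of 18 will be analyzed separately".
- Section 7, Informed Consent: "For the pediatric population, consent will be requested from parents in the same way".

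Two places speak of adults:

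- Section 4, Description of the pathologies being studied, which follows the criteria: "Adult patients will be enrolled, diagnosed with Chronic Pain (pain lasting > 12 weeks".
- Section 5, Enrollment procedure: "Adult patients of both sexes who belong to pain therapy centers with a diagnosis of Chronic Pain". After the definition of chronic pain, the same sentence ends: "regardless of the etiology, modality and age of onset, will be considered eligible for enrollment".

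Section 3 adds how recruitment will open: "Patient enrollment at each center will begin at different times depending on the rollout of the registry and local ethics committee approval".

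**The concern.** Who may be enrolled is a matter for the protocol, and here the answer depends on which section is read. The adult wording is not one stray word. It occurs in two sections, and in Section 5 it is the subject of a sentence that defines eligibility, in the procedure that centres will follow.

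Centres join at different times, each after its own ethics committee has approved, and Section 3 says that the final number of centres cannot be predicted. Many people will therefore read this text independently. A centre working from Section 5 would enrol no minors; a centre working from the inclusion list could. The under-18 data promised in Section 3 might then not exist, or might come only from centres that took the broader reading. Because enrolment is prospective, later analysis cannot recover patients who were never entered.

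**Working it through.** The protocol states no figure that bears on this point, and its sample-size paragraph says that no calculation is required. The check is therefore a comparison of texts plus one subtraction.

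**1. Age statements side by side**

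| Place | Minors in scope? | Form of the statement |
|---|---|---|
| Section 3, Setting | Yes | Paediatric centres expected; under-18 data analysed separately |
| Section 4, Inclusion criteria | Yes, above 4 years | Formal criterion |
| Section 7 | Yes | Parental consent |
| Section 4, Description of the pathologies | Adults named | Statement of who will be enrolled |
| Section 5, Enrollment procedure | Adults named | Statement of who is eligible |

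Three places admit minors and two name adults. No text resolves the difference: the adult wording is not tied to a phase, a type of centre or a subgroup, and no order of precedence is given.

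**2. One patient under both rules**

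Take a 10-year-old with NRS > 4, IASP-defined chronic pain and written consent from the parents.

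- Under the inclusion list with Section 7, the child is eligible.
- Under the Section 5 sentence, the child is not among those eligible.

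Section 5 does not correct itself for a reader who stays within it. It describes consent as the subject signing the form and mentions no parental route.

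**3. Width of the disputed band**

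- If the criterion means past the fourth birthday: 18 − 4 = 14 years of age.
- If it means at least 5 completed years: 18 − 5 = 13 years of age.

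This measures the range in dispute. It says nothing about the number of patients.

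**4. Number of patients affected**

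This cannot be derived. Section 8 expects about 2500 patients from 12 centres, with no split by age, and no section gives an expected number or share of minors.

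**5. Consequence for the analysis**

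Section 8 includes all enrolled patients and does not repeat the age split. The separate under-18 analysis in Section 3 is what keeps minors out of the adult results. If that sentence is followed, the adult results are largely unaffected and the effect is confined to the paediatric cohort.

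**The case against.** The strongest reply is that the intended reading is not in doubt. Only one list is headed as inclusion criteria, and Section 4 introduces it by saying that the criteria should be kept broad. Paediatric centres, a separate under-18 analysis and parental consent would serve no purpose in an adult registry. Neither adult sentence says that minors are excluded. One stands under a heading about pathologies. The other leaves out the NRS criterion, so it is not a complete eligibility rule and may be only a loose summary. A paediatric centre would hardly join and then read the protocol as excluding all its patients. The harm is unquantified, and no objective or endpoint in Sections 2 and 6 is specific to children.

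Much of this stands. The weight of the text does point towards including minors, the risk is more plausible at mixed centres than at paediatric ones, and the harm cannot be sized. But a probable intent is not a stated rule, and the Section 5 sentence does say who is eligible. Followed as written, it leaves the under-18 analysis without data.

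Two side arguments carry little weight. Section 3 has deviations reported to the local ethics committee, so one might say that enrolling a minor complies with one section and is a reportable deviation under another. However, that paragraph describes a request to modify the protocol and does not clearly set up patient-level reporting. The exclusion of patients who cannot sign consent makes no exception for minors, but the parental consent in Section 7 largely explains it.

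**Conclusion.** The concern holds: the current text contradicts itself on age, and nothing in the document settles it. Confidence is high for the contradiction. The harm is a risk rather than a demonstrated effect. It depends on at least some centres or ethics committees applying the adult wording, and the number of patients cannot be computed.

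The scope is limited to minors, a band of 13 or 14 years of age. The adult results are largely safe, provided that the separate under-18 analysis in Section 3 is carried out. The paediatric cohort is exposed to being empty or selected by how each centre read the protocol. The sponsor should correct this, although it does not undermine the registry as a whole.

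**What to change.** The sponsor should choose one age rule and bring Sections 3, 4, 5 and 7 into line with it. This review does not say which rule is right.

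- **If minors are in scope:** replace the adult wording in the Section 4 description and the Section 5 enrolment procedure with the age given in the inclusion criterion. As a minor point, word the exclusion on signing consent so that it agrees with the parental consent in Section 7.
- **If minors are not in scope:** change the age in the inclusion criterion, and delete the paediatric text in Section 3 (centres and separate analysis) and in Section 7 (parental consent).

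Either way the cost is a wording amendment notified to the ethics committees. Neither option adds a visit or a data item. The first changes the eligibility text of the enrolment procedure; under the second, the paediatric centres and the parental consent route fall away. The change should be made before further centres open, since patients missed at enrolment cannot be added by analysis.
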